## **Results:**

We describe the basic clinical characteristics of the patient underwent surgical procedure, and the incidence of primary outcomes (IAPI) and attributable mortality were reported. We will evaluate the performance of the model by assessing its accuracy,

precision, recall, and other relevant metrics. We will compare the predicted outcomes with the actual outcomes to determine the model's effectiveness in correctly predicting the outcome of interest. Additionally, we may also conduct statistical analyses to identify which indicators have the strongest predictive power and contribute the most to the model's performance. The results will be presented and interpreted in the study, providing valuable information about the model's reliability and potential applicability in future scenarios. The secondary outcome of this study is in-hospital mortality, surgical complications in patients during the same hospitalization will also be reported. Additionally, we evaluated the duration of hospital stay and associated costs incurred by patients within this hospitalization period.

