## **2. Methods**

### ***2.1 Study Design***

The proposed study design is a prospective, multicenter, cohort study, which aims to calculate the risk factors that influence the incidence of IAPI. This design allows researchers to observe the natural history of IAPI, and to identify potential risk factors and interventions that may affect the incidence of IAPI.

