### ***2.3 Setting***

The patients will be recruited from the operating rooms of nine tertiary hospitals in China: Affiliated Hospital of Guangdong Medical University (Guangdong), First Affiliated Hospital of Sun Yat-sen University (Guangdong), Foshan First People's Hospital (Guangdong), First Affiliated Hospital of Zhengzhou University (Henan), and The First Affiliated Hospital of Nanchang University (Jiangxi).

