33. Nutritional state (Length of NPO status)
12 hours or <
>12 hours but <24 hours
>24 hours
34. Body Mass Index or weight
<30 kg/m  (normal)
30 kg/m  -35 kg/m  (underweight/obese)
>35kg/m  (morbidly obese)
35. Weight Loss (Weight loss in 30–180 days)
Up to 7.4% weight loss, no change or unknown
Between 7.5% and 9.9% weight loss
≥10% weight loss
36. Age
39 or <
40-59
60 or >
37. Mobility
Not limited, or slightly limited, moves independently
Very limited, requires transfer assistance
Completely immobile, requires full assistance
38. Comorbidity (Identify and add 1 point for each condition)
Smoking/Asthma/Hypertension/Diabetes/Vascular disease/respiratory disease
Intraoperative Risk Factor Score
39. Physical status/American Society of Anesthesiologists pre-anesthesia evaluation score

Healthy and mild systemic disease, no functional limitations
Moderate to severe systemic disease, some function limitation
Moderate to severe systemic disease, constant threat to life and functionally incapacitating or ASA >3
40. Anesthesia
Minimum alveolar concentration (MAC), local
Regional
General
41. Body temperature (98.6°F=37°C)
36.1°-37.8° (body temperature maintained)
>37.8° or <36.1° (+ or -2°) (fluctuated + or ->2°)
>37.8° or <36.1° (+ or - >2°) (maintained + or ->2°)
42. Hypotension
Absent or <10% change in blood pressure
Fluctuating or 11%-20% change in blood pressure
Persistent or 21%-50% change in blood pressure
43. Moisture (Skin under patient)
Remains dry
Some moisture
Pooled or heavy fluid
44. Support surface (Positioning aids, warming blanket, position change)
None/use of blanket over/stationary
Use of aids/blanket under/stationary
Shearing force/added pressure/variable position
45. Position (for surgical procedure)
Lithotomy
Lateral
Supine/Prone
Postoperative Risk Factor Score
46. Length of surgery (Total time from arrival to preoperative and departure from postoperative units)
Up to 2 hours
>2 hours & <4 hours
>4 hours
47. Blood loss
Up to 200 cc
201-400 cc
> 400 cc
Relevance of clinical nursing judgement as a contributing factor
48. Nurses are trained in surgical positions.
49. The nurse assumes the role of leading the surgical position.
50. The nurse executed the surgical positioning in accordance with the predetermined plan.

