#### **4.2 Data analysis**

This study is divided into two distinct sections. The aim of the first part is to create and validate a IAPI risk score for individuals from the whole cohort, predicting their individual IAPI values using a combination of potential predictive variables. The aim of the second part is to evaluate whether the IAPI score is helpful in predicting 90-day mortality in individuals from the whole cohort. We also evaluated the incidence and attributable mortality to IAPI, SSI, and surgical complications in patients admitted for

surgical procedures during the same study period.

All statistical analyses were performed with R (the latest version; R Foundation for Statistical Computing) and Python (the latest version; Python Software Foundation). All tests conducted in this study were 2-tailed, and  $P < 0.05$  was deemed statistically significant.

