After variable selection with RFE, we will be trained potential seven statistical models with centred and scaled selected predictors because of the different scales of the predictors and to ease the intercept of models to the IAPI, including a logistic regression, decision tree, random forest, artificial neural network (ANN), eXtreme Gradient Boosting algorithm (XGBoost), support vector machine (SVM), k-nearest neighbors (k-NN). Logistic regression is suitable for binary classification problems, while decision trees can handle both binary and multi-class problems. Random forests and XGBoost are based on decision trees and are known for their good performance in predicting both continuous and categorical variables. ANNs can be used for nonlinear problems, but they require more time for training. SVM and k-NN are also popular for classification problems, but they require different preprocessing techniques.

To evaluate the performance of each model, we will be using the cross-validation. With k-fold cross-validation, the data is randomly divided into k subsets, and each model is trained on k-1 subsets and tested on one subset. This process is repeated k times, with each of the k subsets being used once as the test set. The average

performance across all k tests is then used as the final performance measure. To assess the degree of potential over-fitting of each algorithm, we will be trained them using a 10-fold 10-repeat cross-validation procedure.

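### The IAPI model ignores hospital, so predictors that differ between hospitals, possibly including nurse items 48-49, can be reported as risk factors because of ordinary hospital differences in IAPI

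*Combined protocol and SAP*

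**What the plan says.** Section 2.3 of the combined protocol and SAP states: "The patients will be recruited from the operating rooms of nine tertiary hospitals in China". Sections 2.3 and 3.1 then name five hospitals, all in China.

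Table 1 in section 3.2 lists the potential predictors. Most are patient or operation characteristics. Items 48-50 concern nursing practice: "Nurses are trained in surgical positions" (48), "The nurse assumes the role of leading the surgical position" (49) and "The nurse executed the surgical positioning in accordance with the predetermined plan" (50). None of the three has response categories or a stated unit (nurse, team, hospital or operation). Section 3.5 has the nurse taking part in each operation collect that patient's data.

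Section 4.2.1 splits the cohort at random into 80% and 20%, selects predictors by recursive feature elimination (RFE), and trains seven models, "including a logistic regression, decision tree, random forest" among them, with 10-fold 10-repeat cross-validation. Section 4.2.2 adds bootstrap intervals from 2000 draws. Neither section mentions a hospital term, hospital-based folds or resampling by hospital. The only cluster term in the plan is a random effect for country, in the mortality analysis of section 4.2.3.

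On use of the results, section 2.1 says the design serves to "identify potential risk factors and interventions that may affect the incidence of IAPI". Section 4.2 sets the testing rule ("All tests conducted in this study were 2-tailed", at P < 0.05). The abstract says further analyses may be done to "identify which indicators have the strongest predictive power".

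**The concern.** Hospitals usually differ in IAPI frequency for reasons the model does not fully capture, such as residual case mix or how readily stage 1 erythema is recorded. If a candidate predictor also differs between hospitals, a patient-level model without a hospital term credits it with part of that difference, and its standard error treats every patient as independent. For an item that takes one value per hospital, the independent units number five or nine, not about 4115.

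The planned safeguards do not expose this. With a random split and random folds, every hospital contributes to training, testing and validation, so an item that partly labels the hospital keeps its apparent value throughout. The country effect in section 4.2.3 does not help: it belongs to another analysis, and every named site is in the same country.

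The nurse items matter most because staff could act on them. A spurious association would rest on a handful of hospital contrasts. Scale items that are scored differently from site to site are exposed in the same way.

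**Working it through.** **1. The plan's own figure.** Section 4.1 gives P = 24, S = 0.9, Cox-Snell R² = 0.051 and incidence 0.139.

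n = 24 / [(0.9 − 1) × ln(1 − 0.051/0.9)] = 24 / (0.1 × 0.05834) = 4114.1, rounded up to 4115. Events: 0.139 × 4115 = 572. Events per parameter: 572/24 = 23.83. All three reproduce. The calculation assumes independent patients.

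**2. Assumptions the documents do not supply.** The ICC is taken as 0.01 to 0.05 on the log-odds scale. Hospitals are of equal size. A null yes/no item is more common in 4 of 9, or 2 of 5, hospitals.

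**3. Approximation.**

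- Hospital variance: τ² = ICC/(1 − ICC) × π²/3, which is 0.033 at ICC 0.01 and 0.173 at ICC 0.05.
- Observed-scale ICC: ρ ≈ p(1−p)τ² / [1 + p(1−p)τ²], with p(1−p) = 0.139 × 0.861 = 0.1197. This gives 0.0040 and 0.0203.
- Design effect: DE = 1 + (m − 1) × ρ × ρx, where m is patients per hospital and ρx is the share of the item's variance lying between hospitals.
- Actual two-sided error: 2 × [1 − Φ(1.96/√DE)].

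*Item constant within hospital (ρx = 1).* Nine hospitals, m = 457: DE = 2.81 and 10.3, error 24% and 54%. Five hospitals, m = 823: DE = 4.26 and 17.7, error 34% and 64%.

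*Item present in 80% versus 40% of patients.* With 4 of 9 hospitals high, mean prevalence is (4 × 0.8 + 5 × 0.4)/9 = 0.578, and ρx = 0.4² × (4/9)(5/9) / (0.578 × 0.422) = 0.16. DE = 1.29 and 2.50, error about 8% and 21%. With 2 of 5 high, ρx = 0.16, DE = 1.51 and 3.60, error 11% and 30%.

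**4. Simulation.** 4115 patients, incidence 13.9%, normal hospital intercepts on the logit scale, 2000 runs per cell. Entries are false-positive rates of the patient-level Wald test at nominal 5%.

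| Null item | 9 hosp., ICC 0.01 | 0.02 | 0.05 | 5 hosp., ICC 0.01 | 0.02 | 0.05 |
|---|---|---|---|---|---|---|
| Constant within hospital | 25% | 39% | 54% | 35% | 48% | 65% |
| 90% vs 10% | 19% | 28% | 47% | 26% | 40% | 57% |
| 80% vs 40% | 8% | 12% | 21% | 10% | 18% | 31% |
| 60% vs 40% | 6% | 6% | 10% | 7% | 8% | 12% |
| Varies only by case | 5% | 5% | 5% | 5% | 4% | 5% |

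At ICC 0 every rate was 4% to 6%, as it should be. A separate set of runs gave 23% to 53% and 34% to 65% for the constant item, and 10% to 20% and 11% to 31% for 80% versus 40%, so the two sets agree to within about two percentage points.

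**5. Effect of allowing for hospital.** A hospital-stratified test returned 4% to 6% in every cell where the item varies within hospital. For a constant item it cannot be computed.

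**6. Size of the spurious effect.** For the constant item the median odds ratio (taken away from 1) was 1.11 to 1.22 with nine hospitals and 1.14 to 1.29 with five, over ICC 0.01 to 0.05. With no clustering it was about 1.06 to 1.07 by chance alone.

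**The case against.** A reader might infer that items 48-49 take one value per hospital, that false nurse-training or positioning risk factors will therefore be reported, and that the items should be removed now. The documents do not support this.

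- **The unit is undefined.** Table 1 gives none, section 3.5 has data collected patient by patient, and item 49 is worded in the same singular form as item 50, which plainly can vary by operation. If the nurse items vary mainly by nurse or case, the inflation is small or absent (bottom rows of the table).
- **Selection is not by P value.** RFE works on predictive gain and stops where the gain tails off. No section specifies coefficient tests for the IAPI model, the P < 0.05 rule is general, and ranking of indicators is only something that may be done.
- **The gain in AUC is often small.** At ICC 0.05 a hospital-constant null item raised random 10-fold AUC in 66% to 68% of runs with nine hospitals and 73% to 74% with five, against about 19% to 21% without clustering. But the median gain was only 0.0005 (nine) or 0.003 (five), exceeding 0.005 in 20% and 40% of runs. With 80% versus 40% prevalence it exceeded 0.005 in at most 2%. RFE would often drop such an item, although RFE itself was not simulated.
- **Hospital differences are partly addressed.** The candidates include age, ASA status, comorbidity, position, duration and blood loss. Section 3.2 requires common training at all centres, and section 4.2.4.1 plans harmonised categories. Only residual hospital variation matters, and the ICC range is assumed.

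These points rule out certainty and rule out removing the items before their unit is known. They do not supply a hospital term. Section 2.1 still sets risk factors as an aim, so any odds ratios or P values taken from the planned logistic model would ignore hospital.

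**Conclusion.** The concern holds in a limited form. The primary IAPI analysis treats patients of five to nine hospitals as independent, and its internal validation cannot reveal a hospital effect carried by a predictor. Candidates that differ between hospitals can therefore be reported as risk factors when they are not. Items 48-49 may be among them, depending on how they are recorded.

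Over an assumed latent ICC of 0.01 to 0.05, the false-positive rate at nominal 5% is about 23% to 53% (nine hospitals) or 34% to 65% (five) for an item constant within hospital, about 10% to 20% or 11% to 31% for 80% versus 40% prevalence, and about 5% for an item that varies only by case. These rates describe a Wald test on a single null item with no other covariates. They are not the probability that RFE keeps the item or that the study reports it. The remedy is a standard and inexpensive one, so the plan should adopt it.

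**What to change.** Amend sections 4.2.1 and 4.2.2 as follows.

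1. Include a hospital intercept (random or fixed) in the logistic model used to report odds ratios and P values for IAPI risk factors. Use the average intercept when the score is applied to a new patient.
2. State the unit on which items 48-50 are recorded and check how much each varies within hospital. Only if an item proves constant or nearly constant within hospital, leave it out of patient-level selection, report it by hospital, and do not describe it as a risk factor or intervention. A fixed hospital intercept could not estimate such an item in any case, and a random one would leave only five to nine units of information.
3. Add leave-one-hospital-out cross-validation for all candidate models, as a check on the random folds. This also covers the algorithms that carry no hospital intercept.

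The cost is some extra analysis, slightly wider intervals for some odds ratios, and accepting that the study says little about items that vary only between hospitals. Hospital should already be known from site-based data entry (section 3.6), so no extra patients or data are needed.

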## 51. Other variables (at the discretion of the nurse/doctor)

### 3.3 Schedule of Events

The events schedule comprised three sequential stages: recruitment and screening, baseline assessment, and outcome follow-up. The primary endpoint of this study is to evaluate the clinical outcomes three months post-surgery, its follow-ups should be office visits, but telephone contact will be allowed. Data collected during all follow-up visits will include IAPI, SSI, surgical complication, death. Original source documents must be submitted for any clinical events (death, IAPI, SSI, surgical complication, within 3 months).

**Table 2 Schedule of Events in the observational cohort for this study.**

	Recruitment & screening	Baseline assessments	Follow up						
			0.5 hours	2 hours	24 hours	48 hours	72 hours	7 days	3 months
Informed consent 	X	X							
Inclusion/exclusion criteria	X	X							
Demography/ Surgical procedures	X	X							
Potential predictor variables		X							
IAPI			X	X	X	X	X	X	X
SSI						X	X	X	X
Surgical complication 			X	X	X	X	X	X	X
Death			X	X	X	X	X	X	X

Abbreviation: IAPI: intraoperatively acquired pressure injure, SSI: surgical site infections.

 The informed consent should be signed prior to the surgical procedures, but it can be signed after the surgical procedures in the urgent situation.

 The surgical complications in patients during the same hospitalization will also be observed, as defined by the Clavien-Dindo classification.

### **3.4 Recruitment of subjects**

One day prior to the surgical procedure, the perioperative nurse/investigator informed the prospective surgical participant about their potential enrollment in the observational cohort for this study. In exceptional circumstances, assessment of the patient before admission into the operating room on the day of surgery procedure remains permissible. Prior informed consent was duly obtained from either the patients themselves or their legal guardians.

### **3.5 Data collection**

The clinical data of each surgical patient were collected by itinerant nurses who actively participated in the surgical procedure, and the data they collected were promptly submitted post-operation. Endpoint follow-up was conducted by dedicated personnel through telephone interviews, web-based data completion, or other appropriate methods.

### **3.6 Data management and storage**

The study incorporates three pre-determined key components. The network-based data will be programmed to monitoring: adherence to inclusion and exclusion criteria, homogeneous training of evaluators, and timely completion of all required data collection (without any missed visits, studies or specimens).

The itinerant nurses will determine the form content by identifying the minimal set of measurements for specified variables, selecting documentably valid and reliable

measurements (if more than one candidate), and developing, testing, and assessing reliability of new measures as required. Experienced data coordinating center (setting in participating institutions of principal investigator) staff will then order and format items to ensure clarity, smooth flow, and minimize missing information using clear skip patterns, consistent coding for all close-ended items, and standard footers to identify form name, version date, and page number. Standard modular data forms will be identified and developed for use in both the trial and registry as needed.

The Case Report Forms (CRF) will be developed as an online electronic form, enabling investigators from individual sites to access and input data via the internet.

The data coordinating center will assume responsibility for providing training to the investigator and clinical site personnel as required. Designated monitors will receive appropriate training to effectively monitor study progress, encompassing various aspects such as adherence to protocol and accurate completion of electronic Case Report Forms (eCRFs). To ensure consistent implementation of the standard protocol, data collection, and management across sites, the data coordinating center will facilitate comprehensive on-site or web conference-based training sessions over a period of one week. These sessions aim to cover essential components of clinical staff training including: (1) Familiarization with Registry Protocols; (2) Proficiency in database systems and eCRF for local web-based data entry; (3) Competence in medical record abstraction; (4) Skillful specimen/media collection and handling; (5) Effective data handling techniques; (6) Interview techniques refinement; and finally, (7) Clear understanding of quality control expectations.

The data coordinating center will ensure that all study data is protected and maintained securely during the observation period. All observation data, including investigational data and medical records, will be stored in a secure location accessible only by authorized personnel.

The study monitor will conduct periodic site visits to review the progress of the study, verify data quality, and ensure compliance with the protocol and applicable regulations. The study monitor will also conduct consecutively enrolled data audits to ensure the accuracy and completeness of the data.

During the site visits, the study monitor will review the Investigator's study files, including subject consent forms, screening records, and observation-related correspondence. The study monitor will also examine the medical records of study subjects to confirm their eligibility, the conduct of procedures, and the treatment provided.

The study monitor will communicate any observations or concerns to the Investigator/site and data coordinating center in a timely manner. The Investigator/site will have the opportunity to respond to these observations or concerns and provide explanations or clarifications.

In the event of non-compliance with the protocol or applicable regulations, the trial monitor will work with the Investigator/site and data coordinating center to develop and implement corrective actions to address the issue. The trial monitor will continue to monitor the trial until the issue is resolved and will report back to the data coordinating center on the status of the corrective actions taken.

The study monitor's responsibilities do not end with the completion of the trial.

After the study is complete, the trial monitor will assist in closing out the trial, including data verification, final report preparation, and auditing of study records.

## 4. Data Analysis

### 4.1 Sample size

The primary outcome of this study is IAPI in patients who underwent surgery procedure.

The fixed position of surgical patients in the surgical procedure, and the occurrence of IAPI risk is time-dependent, which it is positively correlated with the advancement of time and the occurrence of IAPI events in surgical patients. For time-to-event outcomes, ensure the sample size is enough to: Estimate the overall outcome proportion with sufficient precision at one or more key time-points in follow-up; Target a shrinkage factor of 0.9; Target small optimism of 0.05 in the apparent  $R^2_{\text{Nagelkerke}}$ . The formula provided by Riley et al. is as follows:

Time-event-outcome, the sample size (number of participants, n) required to achieve the expected uniform contraction coefficient S can be expressed as:

$$n = \frac{P}{(S-1)\ln\left(1 - \frac{R_{cs}^2}{S}\right)}$$

To calculate the sample size, to ensure that the expected optimistic value of  $R^2$  (i.e.,  $R_{cs}^2/\max(R_{cs}^2)$ ) has a smaller expected optimism. For time-event-outcome, the first step is to calculate the contraction coefficient corresponding to the expected optimistic value in  $R^2_{\text{Nagelkerke}}$ :

$$S = \frac{R_{cs}^2}{R_{cs}^2 + \delta\max(R_{cs}^2)}$$

The recent randomized controlled trial results showed an incidence of IAPI (stage I and above) of 13.9%, assuming 0.05 acceptable difference in apparent & adjusted

R-squared. The study used the R4.1.2 software (pmsampsize package) to estimate the minimum sample size required to develop the new model. Minimum sample size required for new model development is 4115, with 572 events (assuming an outcome prevalence = 0.139) and an Events per Predictor Parameter (EPP) is 23.83. In addition, according to the pre-model design requirements, the total sample was divided into 80% samples for the development of the new model and 20% samples for the validation of the model. This means that a total of 5144 cases are required. Considering a possible 10% loss of follow-up, the minimum sample size required for the prediction model was 5658 cases.

```
NB: Assuming 0.05 acceptable difference in apparent & adjusted R-squared
NB: Assuming 0.05 margin of error in estimation of intercept
NB: Events per Predictor Parameter (EPP) assumes prevalence = 0.139
```

	Samp_size	Shrinkage	Parameter	CS_Rsq	Max_Rsq	Nag_Rsq
Criteria 1	4115	0.900	24	0.051	0.553	0.092
Criteria 2	833	0.648	24	0.051	0.553	0.092
Criteria 3	184	0.900	24	0.051	0.553	0.092
Final	4115	0.900	24	0.051	0.553	0.092
		EPP				
Criteria 1	23.83					
Criteria 2	4.82					
Criteria 3	1.07					
Final	23.83					

```
Minimum sample size required for new model development based on user inputs = 4115,
with 572 events (assuming an outcome prevalence = 0.139) and an EPP = 23.83
```

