### **Methods:**

We will use a pre-set observational assessment scale that consists of 24 indicators to construct the predictive model in this study. In addition to these pre-set indicators, the researchers will also collect other relevant indicators that they believe may contribute to the predictive model. Primary outcome was incidence of IAPI of any stage at 7 days from operating room admission. Secondary outcomes were in-hospital mortality (follow-up endpoint is 3 months after surgical procedure), surgical complication, and hospitalization costs. The prospective cohort study dataset is divided randomly into two

subsets: a training group (80% of the data) and an internal validation group (20% of the data). The training group is used for model development, while the internal validation group remains untouched until later stages. In model development, researchers can explore different variables and test various machine learning algorithms, such as logistic regression, artificial neural network (ANN), XGBoost, support vector machine (SVM), k-nearest neighbors (k-NN), naive Bayes, gradient boosting machines (GBM), AdaBoost, Gaussian mixture model (GMM), and support vector regression (SVR). They can train and optimize these models using the training dataset. After training the models on the training dataset, researchers can evaluate their performance using appropriate evaluation metrics (e.g., accuracy, precision, recall, F1-score, area under the receiver operating characteristics curve). Based on the evaluation results, we refine the model by tweaking hyperparameters, feature selection, or employing techniques like cross-validation or grid search. This iterative process aims to find the best-performing model configuration. Once the model is optimized using the training dataset, it is then evaluated on the internal validation dataset. This evaluation serves as an unbiased assessment of the model's performance on unseen data, providing an estimate of its ability to generalize. Based on the performance on the internal validation dataset, to choose the best-performing model as the final predictive model.

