#### 3.2 Data collection tools and instruments

The data collection will be facilitated through a network-based data infrastructure, where in the potential predictor variables are comprehensively described in [Table 1](#). Further details can be accessed on the website <https://www.wjx.cn/>. Prior to sample inclusion, data collectors at all participation centers underwent mandatory homogenization training. The clinical follow-up will be conducted at 0.5, 2, 24, 48, and 72 hours post-surgical procedure, as well as at the three-month mark following the completion of the surgical procedure. The investigator has the flexibility to carry out these follow-ups either through ward visit, telephone communication or follow-up appointments for outpatient care.

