**Table 1: Potential predictor variables**

Braden scale
1. Sensation
Completely limited: unresponsive (does not moan, flinch or grasp) to painful stimuli because of diminished level of consciousness or sedation OR a limited ability to feel pain over most of body

surface.
Very limited: responds only to painful stimuli; cannot communicate discomfort except by moaning or restlessness OR has a sensory impairment that limits the ability to feel pain or discomfort over half of the body.
Slightly limited: responds to verbal commands but cannot always communicate discomfort or need to be turned OR has some sensory impairment that limits ability to feel pain or discomfort in one or two extremities.
No impairment: responds to verbal commands; has no sensory deficit that would limit ability to feel or avoid pain or discomfort.
2. Skin moisture
Constantly moist: skin is kept moist almost constantly by perspiration, urine etc; dampness is detected every time patient is moved or turned
Moist: skin is often, but not always, moist; linen must be changed at least once a shift
Occasionally moist: skin is occasionally moist, requiring an extra linen change approximately once a day
Rarely moist: skin is usually dry; linen changed only at routine intervals.
3. Activity
Bedfast: confined to bed
Chairfast: ability to walk severely limited or nonexistent; cannot bear own weight and/or must be assisted into chair or wheelchair.
Walks occasionally: walks occasionally during day but for very short distances, with or without assistance; spends majority of each shift in bed or chair.
Walks frequently: walks outside the room at least twice a day and inside room at least once every 2h during waking hours.
4. Mobility
Completely immobile: does not make even slight changes in body or extremity position without assistance.
Very limited: makes occasional slight changes in body or extremity position but unable to make frequent or significant changes independently.
Slightly limited: makes frequent, though slight, changes in body or extremity position independently
No limitations: makes major and frequent changes in position without assistance
5. Nutritional status

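### The sample size rests on 24 predictor parameters that the plan neither lists nor codes, while the pool to be screened is larger and open, so a shrinkage factor of 0.9 and 23.83 events per parameter are not supported

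*Combined protocol and SAP*

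**What the plan says.** Section 4.1 sizes the development set with the Riley criteria, run in pmsampsize. One aim is "Target a shrinkage factor of 0.9". The printed output uses 24 parameters and a Cox-Snell R² of 0.051. The text gives the result: "Minimum sample size required for new model development is 4115, with 572 events (assuming an outcome prevalence = 0.139"). The output repeats it, "with 572 events (assuming an outcome prevalence = 0.139) and an EPP = 23.83". An 80/20 split raises the total to 5144, and a 10% loss allowance raises it to 5658.

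The number 24 has one visible origin, the abstract: "We will use a pre-set observational assessment scale that consists of 24 indicators to construct the predictive model in this study". The next sentence widens the pool: "the researchers will also collect other relevant indicators that they believe may contribute to the predictive model".

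Section 3.2 says that "the potential predictor variables are comprehensively described in" Table 1 and refers to a website for further details. The table is headed "Table 1: Potential predictor variables". It has 50 numbered items, taken from five scales plus three nursing items, and ends with an open row: "51. Other variables (at the discretion of the nurse/doctor"). No subset of 24 is marked.

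Section 4.2.1 describes RFE as beginning with every available feature and removing the least relevant in turn. Section 4.2.4.1 allows predictors to be harmonised and coded as quartiles or as two categories. Section 3.6 allows the form to be cut to a minimal set. None of these sections fixes a list, a coding or a parameter count.

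**The concern.** In this formula P counts every candidate parameter examined, not those left after selection. RFE therefore cannot bring the count down to 24 after the fact. If more than 24 parameters are screened, the expected shrinkage factor at 4115 patients falls below 0.9 and the events per parameter fall below 23.83.

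This criterion sets the size of the whole study: criterion 1 gives 4115, against 833 and 184 for the other two. The point bears on the logistic model, which section 4.2.4.2 presents as a route to a points score. Reported as they stand, the two figures could overstate how well that score is protected against overfitting.

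**Working it through.** **Inputs** (section 4.1 and its output): P = 24; S = 0.9; R²cs = 0.051; δ = 0.05; prevalence 0.139; 80% development share; 10% loss.

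**The plan's own figures**

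- Criterion 1: n = P / [(S − 1) ln(1 − R²cs/S)]. With ln(1 − 0.051/0.9) = −0.058336, n = 24 / (0.1 × 0.058336) = 4114.1, rounded up to 4115. Agrees.
- Maximum R²cs = 1 − (0.139^0.139 × 0.861^0.861)² = 0.5535. Agrees with 0.553.
- Criterion 2: S = 0.051 / (0.051 + 0.05 × 0.5535) = 0.648, which gives n = 833. Agrees.
- Criterion 3: (1.96/0.05)² × 0.139 × 0.861 = 183.9, rounded up to 184. Agrees.
- Events: 4115 × 0.139 = 572; 572/24 = 23.83. Agrees.
- Total: 4115/0.8 = 5144. Agrees.

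**Other parameter counts.** At S = 0.9 each parameter needs 1 / (0.1 × 0.058336) = 171.42 patients. The third column solves the same formula for S at n = 4115.

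| P | How it could arise | S at n = 4115 | Events per parameter | Development n for S = 0.9 |
|---|---|---|---|---|
| 24 | as planned | 0.900 | 23.8 | 4115 |
| 25 | the 24 plus one added indicator | 0.896 | 22.9 | 4286 |
| 27 | strict merge of Table 1 | 0.889 | 21.2 | 4629 |
| 34 | looser merge, or 5 of the 24 in quartiles | 0.864 | 16.8 | 5829 |
| 50 | every Table 1 item as one term, duplicates kept | 0.813 | 11.4 | 8572 |

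The counts 27 and 34 are my own readings of Table 1, not figures from the plan.

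- *34 by merging:* pool the repeated items for mobility (4, 14, 21, 27, 37), activity (3, 20), age (8, 23, 36), BMI or weight (10, 24, 34), continence (13, 22, 31), mental state (19, 26), skin (9, 25), nutrition (5, 30), weight loss (11, 35) and length of surgery (15, 46). That removes 16 of the 50.
- *34 by coding:* a variable in quartile categories uses three parameters instead of one, so five such variables give 24 + 2 × 5 = 34.
- *27:* also pool activity with mobility, 33 with nutrition, 2 with 43, 18 with 39, 28 with 42, and 12 with 16 and 38. That removes 7 more.

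**Sensitivity to R²cs.** Rounding of 0.051 (0.0505 to 0.0515) moves S by at most 0.002. For S = 0.9 to hold at n = 4115, R²cs would have to be 0.057, 0.071 or 0.103 for P = 27, 34 or 50.

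**Room in the planned total.** With no loss at all, 5658 × 0.8 = 4526, and 4526/171.42 = 26.4, so 26 parameters are supported.

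**Loss allowance.** 5144 × 1.10 = 5658, but keeping 5144 after 10% loss needs 5144/0.90 = 5716. The planned 5658 tolerates 1 − 5144/5658 = 9.1% loss. At 10% loss the development set is 5658 × 0.9 × 0.8 = 4074 (566 events), and S for P = 24 is 0.899.

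**The case against.** The strongest reply is that 24 may well be a real, reduced list. Table 1 repeats age three times and mobility five times, and the plan intends to harmonise such items. The full item sets are also needed to score the five comparator scales in section 4.2.2, so the presence of 50 items does not prove that all 50 enter RFE. If the nursing items 48–50 are dropped from the strict merge to 27, exactly 24 remain. This shows that 24 is reachable. It takes a merge that the plan does not state, with one parameter per construct. The website cited in section 3.2 may hold the list, but I could not see it.

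On coding, section 4.2.1 says that selected predictors are centred and scaled, which suggests one numeric term each. That text concerns predictors already selected and does not limit the pool screened. It also sits beside the quartile option in section 4.2.4.1, so the coding remains ambiguous.

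On size, a drop from 0.900 to 0.896 is trivial in itself, and with little loss there is room for 26 parameters. Both statements are true. But that room disappears at the 10% loss the plan assumes, and nothing caps the count. Every shortfall is also conditional on R²cs = 0.051; a higher value would remove it. That stands as a limit on the magnitude, though the plan gives no basis even for 0.051.

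Finally, the inflexion-point stopping rule, the repeated 10-fold cross-validation, the 20% validation set and the calibration slopes do address overfitting. They do not make the stated shrinkage factor or events per parameter correct for a larger pool.

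**Conclusion.** The concern holds, and the plan should be changed. The calculation is correct for 24 parameters, but the screening described is not restricted to 24, so the stated S = 0.9 and 23.83 events per parameter are unsupported rather than shown to be wrong. Over the illustrative range of 25 to 50 parameters, S at 4115 patients runs from 0.896 to 0.813, and the development n needed for 0.9 runs from 4286 to 8572.

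Confidence is high that the list, coding and cap are missing from this document. The size of any shortfall is uncertain: it depends on the true parameter count and on R²cs = 0.051, and it applies to the logistic model only. The loss allowance is a minor slip with almost no effect on S.

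**What to change.** Before outcome data are examined, choose one of two routes.

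- **Cap the pool.** Name and code at most 24 candidate parameters for RFE. Declare all other items, including item 51, exploratory or collected only to score the comparator scales.
- **Restate the figures.** Give the actual candidate parameter count in section 4.1, with the S and events per parameter that it yields at n = 4115. Shrinkage or penalisation of the logistic model could be added but is optional.

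Possible wording: *The candidate parameters entered into RFE are the [P] listed in Table [x] with the coding shown; at n = 4115 and R²cs = [value, with its basis] this gives S = [..] and events per parameter = [..].*

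Under either route, state where 0.051 comes from; if it changes, rerun the calculation. In a footnote, either give 5716 as the total or say that 5658 allows for 9.1% loss.

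The cost is protocol and SAP wording, one coded table and a rerun of pmsampsize. The price is a smaller candidate pool or less favourable stated figures. Restating the figures needs no extra patients; adopting 5716 would add 58.
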